4.7.1 Sample Size

The sample size determination of 50 per group was based on a review of the literature and feasibility. [name] has provided justification for a lack of sample size analysis (see Appendix I).

5.0 RISKS AND BENEFITS

5.1 Potential Benefits to Subjects

Participants enrolled in the study may have better pain relief if they are randomized to the psoas compartment block group. However, this has not been proven and patients may receive no direct benefit from inclusion in this study. Knowledge gained in this study may provide benefit to future patients undergoing total hip arthroplasty with an anterior approach if benefits of one technique can be identified.

5.2 Potential Risks to Subjects

The risks of participating in this study include the same risks normally associated with hip surgery whether the patient is in the study or not. The risks directly related to the techniques being studied are as follows:

Standard of Care Risks

Less Frequent (occurring from 1% to 10% of the time):

- Low blood pressure
- Nausea
- Vomiting
- Low heart rate
- Anxiety
- Numbness of skin
- Pain
- Itching
- Fever
- Dizziness
- Chills
- Reduced sensation of your hip area (where the surgery will take place)
- Block failure (this is when the block does not work, thus causing pain after surgery)

Rare (occurring less than 1% of the time):

- Runny nose
- Allergic reaction
- Temporary or permanent nerve damage
- Infection
- Perioperative injury secondary to numbness or weakness, such as falling if trying to walk before the block wears off

With any procedure, unusual, unexpected or previously unreported side effects may occur. Risks will be assessed throughout the course of the study.

There is also a rare risk of breach of confidentiality. Every effort will be made to maintain patient privacy, however this cannot be guaranteed.

6.0 DATA SAFETY MONITORING AND ADVERSE EVENTS

6.1 Plan for Monitoring and Safety Review

An internal safety monitoring committee will be assembled. Members of group will include a scientific reviewer, two clinicians, and a biostatistician for an independent review of adverse event data provided by the investigator. Members invited to participate in the group are independent of the study. The scientific reviewer is [name]. The clinicians are [name], and attending anesthesiologist, and [name], NP who works at MOI with adult reconstruction patients. The group will meet twice throughout the course of the study to monitor safety, recruitment, subject eligibility, adherence to treatment plan, documentation of dropouts and adverse events. The first meeting will be after 30 patients have completed the study. The second meeting will be after 75 patients

have completed the study. Enrollment will continue while these meetings are being planned and taking place. Members will receive a composite of the collected data including complications and adverse events broken down by study group from the study investigators to review before the meeting. One member will be responsible for taking minutes at the meeting. Reports from all meetings will be presented to the study investigators who will be responsible for reporting the data to the HIC.

6.2 Risk Monitoring and Adverse Event Reporting

An adverse event (AE) is any noxious, unintended, or untoward medical occurrence that may appear or worsen in a subject during the course of a study. A serious adverse event (SAE) is any AE which:

- Results in death
- Is life-threatening (i.e., in the opinion of the investigator the subject is at immediate risk of death from the AE)
- Requires inpatient hospitalization or prolongation of existing hospitalization
- Results in persistent or significant disability/incapacity (a substantial disruption of the subject's ability to conduct normal life functions)
- A medical event that may jeopardize the subject or require medical or surgical intervention

The severity of adverse events (AEs) will be graded on a scale of 1 to 5 according to the National Cancer Institute (NCI) Common Terminology Criteria for Adverse Events ([The NCI Common Terminology Criteria for Adverse Events, Version 4.0 [NCI CTCAE]). The PI will determine the relationship between the administration of the block and the occurrence of an AE/SAE as unrelated, probably not related, probably related, or definitely related.

The participant will be monitored for risks and AEs in the hospital as standard of care. The PI and surgeon co-investigators will be responsible for tracking the occurrence of AEs while the patient is in-hospital. After discharge through the first follow-up appointment the patient will be monitored for hospital readmissions and asked to notify the PI of the occurrence of any AEs. A final assessment of complications and AEs will be made at a 3 week follow-up visit in the clinic (Michigan Orthopaedic Institute).

AEs of grade 4 or 5 will be reported to the HIC within 7 days. They will also be reported to the chair of the internal safety monitoring committee within 7 days and he will make a recommendation as to whether the study should continue.

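### The seven-day safety report is triggered by severity grade alone, so a serious adverse event graded below 4 gets no prompt report and, after the second committee meeting, has no stated route to the committee

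*Combined protocol and SAP*

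**What the plan says.** Section 6.2 sets up two classifications of adverse events.

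- **Seriousness** is defined by outcome. Besides death and immediate threat to life, the criteria are "Requires inpatient hospitalization or prolongation of existing hospitalization", "Results in persistent or significant disability/incapacity" and "A medical event that may jeopardize the subject or require medical or surgical intervention". None of them carries a grade.
- **Severity** is separate: "The severity of adverse events (AEs) will be graded on a scale of 1 to 5", by reference to CTCAE version 4.0.

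The expedited rule uses only the second: "AEs of grade 4 or 5 will be reported to the HIC within 7 days". The next sentence applies it to the committee: "They will also be reported to the chair of the internal safety monitoring committee within 7 days". The chair's recommendation on whether the study continues is attached to those same events. After its definition, the term SAE appears only where the investigator judges relatedness. The section also says that after discharge "the patient will be monitored for hospital readmissions".

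Section 6.1 supplies the periodic route. The committee meets twice, first after 30 completers; then "The second meeting will be after 75 patients" have completed. Before each meeting it receives the collected data, including adverse events of any grade by study group, and the investigators pass the meeting reports to the HIC. Enrolment is not paused. No later meeting or closing report is described. Section 4.0 gives the total as 100 patients.

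**The concern.** A protocol normally defines seriousness in order to decide which events are reported promptly. Here the definition drives no reporting step. Three of its five criteria require neither death nor immediate risk of death, and nothing says that every SAE is grade 4 or 5. An investigator who follows the rule exactly could therefore record a readmission as an SAE, grade it below 4, and owe no seven-day report.

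The protocol foresees events of this kind. It tracks readmissions, collects DVT, falls and infection as major complications (section 4.6), and plans a subgroup analysis that leaves out patients who needed further surgery (section 4.7). At stake is how soon the independent reviewers learn of such events while patients are still being randomized and, late in the trial, whether the protocol gives them any means of learning at all.

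**Working it through.** The plan states no event rate and no safety power figure, so there is no figure of its own to reproduce. The check sets the reporting routes side by side and then sizes the gap.

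**Step 1. Routes for an event (sections 6.1 and 6.2)**

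| Event | Within 7 days | At the meetings | After the second meeting |
|---|---|---|---|
| Grade 4 or 5, SAE or not | HIC and chair | Yes | HIC and chair, within 7 days |
| SAE graded below 4 | None stated | Yes, then to the HIC through the meeting report | None stated |

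The gap is confined to the second row. For patients covered by a meeting it is a delay; after the second meeting no route is stated.

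**Step 2. Length of the delay.** An event just after the first meeting waits for the second: 75 − 30 = 45 completers. An event early in the trial waits for up to 30.

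**Step 3. Patients after the last meeting.** At most 100 − 75 = 25. Two things lower this:

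- Meetings are set by completers. With dropout d and no replacement, 100(1 − d) − 75 gives 20 at 5%, 15 at 10% and 5 at 20%. These dropout rates are assumptions.
- Enrolment continues while the meeting is arranged, so the data sent may include some patients beyond the 75th.

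**Step 4. Chance that the late gap matters.** Let p be the per-patient probability of an SAE graded below 4. The documents give no value, so p is assumed. With independent patients, the chance of at least one among n is 1 − (1 − p)^n.

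| p | n = 25 | n = 15 |
|---|---|---|
| 1% | 1 − 0.99^25 = 22% | 14% |
| 2% | 1 − 0.98^25 = 40% | 26% |
| 5% | 1 − 0.95^25 = 72% | 54% |

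Section 5.2 offers the only nearby figures: nerve damage and injury from falling are each listed among risks below 1%. The SAE definition covers more than these two, so a total of 1% or above is possible, but nothing in the documents fixes it.

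**Step 5. Effect of the change.** If every SAE goes to the chair within seven days, the number of patients whose lower-grade SAEs have no stated route falls from at most 25 to 0.

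**The case against.** The strongest reply is that little is lost. Adverse events of every grade are assessed through the three-week visit, complications are outcome variables, and the committee sees all grades by group at both meetings, with the HIC informed afterwards. This stands for patients covered by the meetings. A reader might infer that lower-grade SAEs go unreported throughout; the documents do not support that. For most of the trial the issue is timing. Capture in the study data does not, however, supply a route to the committee after the second meeting.

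Second, 25 is a ceiling, and the top of the probability range rests on an unsourced 5% rate. Both points stand, which is why the figures above are given as a range and with a smaller n.

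Third, a reader might infer that these are the events most likely to distinguish the two techniques. Section 5.2 lists the risks for both together and gives no difference between groups, so that inference has no basis here.

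Fourth, whether a particular readmission or nerve injury would be graded below 4 depends on a grading table that is cited but not reproduced. The point does not need it: the text defines seriousness and severity separately and never equates them. Reporting rules that the HIC may apply outside this protocol cannot be checked, so the finding is only that this protocol states no such report.

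Finally, extending the rule has a price. The criterion on medical or surgical intervention is broad, and section 5.2 lists low blood pressure, nausea and vomiting at 1% to 10%; treated cases might qualify. This stands and is counted as a cost.

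**Conclusion.** The point holds as a gap between the SAE definition and the reporting trigger in section 6.2, made wider by the absence of any review after the second meeting in section 6.1. An SAE graded below 4 is delayed by up to 45 completers between meetings; for at most 25 of 100 patients the protocol states no route to the committee for it. At an assumed 1% to 5% per patient, the chance of at least one such event among 25 is 22% to 72%; with 15 patients it is 14% to 54%. These probabilities illustrate the scale and are not estimates.

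A reader might go further and conclude that serious events late in the trial would never reach the committee. That is too strong: grade 4 and 5 events go to the chair within seven days throughout. The primary analysis is not affected. This is a worthwhile, inexpensive correction to safety oversight.

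**What to change.** Reconcile the definition and the trigger in section 6.2, and add a closing step to section 6.1:

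1. Replace the expedited rule with: *Any event meeting the SAE definition above, and any AE of grade 4 or 5, will be reported within 7 days to the HIC and to the chair of the internal safety monitoring committee.*
2. Add: *Once the last patient has completed the 3-week visit, the committee will receive a final composite of AEs and SAEs by study group.* Individual reports go to the chair only; this gives the whole committee the comparison by group for patients after the second meeting.

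The cost is two sentences, one further data transmission, and additional seven-day reports. How many cannot be said from the documents, because the intervention criterion may take in treated minor events. The sponsor may wish to clarify how that criterion is to be read when making the change. No new visits or assessments are needed.

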8.0 APPENDIX I

Table I. Schedule of Events

Study Procedures	Screening	Surgery	3 hours postop	POD1 9 AM	POD1 5 PM	POD2 9 AM	POD2 5 PM	3 weeks postop
Visit Windows	-21 to 0 days	N/A	± 1 hours	± 2 hours	± 3 hours	± 2 hours	± 3 hours	± 1 week
Review inclusion and exclusion criteria	X							
Informed consent review and signature	X*							
Study Group Determination (Randomization)	X*							
Intervention (psoas block or periarticular injection)		X						
Collect resting pain score	X ^a		X	X	X	X ^b	X ^b	X
Collect pain with ambulation	X ^a			X ^c	X ^c	X ^{b,c}	X ^{b,c}	X ^c
Quality of Recovery-40 assessment				X		X ^b		
Opioid-related symptom distress scale assessment				X		X ^b		
Assess for adverse events			X	X	X	X	X	X

POD = postoperative day

*Consent will happen before any study procedures or assessment are done and randomization will occur at that time

a. Collected as standard of care in the clinic

b. If patient has been discharged before this time point assessments will not be collected

c. If patient is not ambulating they will have the option of selecting 'N/A'

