4.6 Data Collection

- Primary outcome variable: VAS Pain scores measured at times in Appendix I: Table I
- Secondary outcome variable: Total amount of opioid usage in-hospital (and with 24 hours and 24-48 hours postoperatively)

Demographic and Operative Variables

- Sex
- Age
- Race
- BMI
- ASA score
- Comorbidities, as recorded by anesthesiology
- Date of Surgery
- Time of Surgery
- Laterality (left/right)
- Operative Time (skin incision to skin close, mins)
- Estimated Blood Loss (mL)
- Intraoperative Complications (fracture, bleeding events, etc.)

Outcomes Variables

- Narcotic Use (expressed in oral morphine equivalent units)
- Non-narcotic pain medication usage
- Major Postoperative Complications (DVT, Falls, Infection, etc.) through first postoperative visit
- Units of blood transfused
- Complications related to block/anesthetic
- VAS Resting Pain Scores
- VAS Ambulating Pain Scores
- Time of First Physical Therapy Session
- Length of Hospital Stay (Days)
- Readiness for discharge (days), requiring the following:
 - A pain score of <4 (numeric rating scale) without non-oral narcotics

- Normal eating
- Minimal nausea
- Urination without a catheter
- A dry surgical wound
- No acute medical problems
- The ability to independently transfer and walk 100 feet
- Stable vitals

Pain will be measured on a numeric Likert scale, rating the pain from 0 (none) to 10 (maximal). Scores will be collected at 3 hours postoperatively, in the morning and afternoon on postoperative day one and two and at the post-operative clinic visit. The patient will record their pain on a data collection form that is given to them at each time point. Pain will be recorded for when the patient is at rest and when the patient is ambulating. On postoperative day one and postoperative day two the patient will be asked to fill out the Quality of Recovery Score [Myles] and Opioid-Related Symptom Distress Scale [Apfelbaum, Yadeau] (Appendix I: Table I).

All pain medications will be prescribed per standard of care. Pain medication usage in-hospital will be recorded from Epic. All opioid consumption will be converted to oral morphine equivalents in milligrams. All demographic and operative variables will also be collected for each patient from electronic medical records.

Readiness for discharge will be assessed in both the morning and evening of each postoperative day.

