4.7 Statistical Analyses

A table of descriptive summaries on demographic and operative variables by treatment group will be prepared (means and standard deviations if normally distributed, median and range if not normally distributed, counts and percentages for categorical variables); inference procedures which are consistent with the chosen variable summaries will be used to compare treatment groups.

Before analyzing continuous variables, data sets will be assessed for normality using a Shapiro-Wilk Test and equal variance using the Levene-test. For normal data an independent Student's t-test will be used to compare means, and a Mann-Whitney Rank Sum Test will be used for data that is not normally distributed. The two treatment groups will be compared on categorical variables using the Chi-Square test or a Fisher Exact test for low frequency occurrences.

VAS Pain scores (resting, ambulating) will be compared between groups at each time point using a Mann-Whitney Rank Sum test. A Bonferroni correction will be used to

account for repeated measures and control for a Type I error. A p -value below $.05/6 = .0083$ at each individual postoperative time point will be considered statistically significant. Opioid usage will be compared for total in-hospital as well as broken down by use a 24 hours and use from 24-48 hours using the Mann-Whitney Rank Sum test. A p -value below $.05/3 = .017$ at each individual postoperative time point will be considered statistically significant. Composite scores and subscores of the Quality of Recovery-40 and Opioid-related Symptom Distress Scale, as well as the time to readiness for discharge, will be compared between groups with the t -test or Mann-Whitney Rank Sum test as appropriate.

For all other tests which do not include Bonferroni adjustment, a two-sided p -value < 0.05 will be considered statistically significant. Missing data will be treated as such; there will be no imputation. An exploratory subgroup analysis will also be performed, excluding patients with longer than 3 day stay or patients that required additional surgical intervention. Confidence intervals for the difference in means/medians/odds ratios between the two groups will also be calculated where appropriate. Graduate-trained engineers will analyze data with SPSS statistical software (SPSS Version 20.0, IBM, Inc).

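### Resting pain on postoperative day 2 is not collected after discharge, so two of the six primary tests may compare only patients still in hospital

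*Combined protocol and SAP*

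**What the plan says.** Section 2.0 makes resting pain the primary objective. Section 4.6 defines the primary outcome as pain scores at the Table I times. Section 3.0 counts the hypothesis as met if the block is better at any one or more of six times. In Table I these are 3 hours, POD1 9 AM and 5 PM, POD2 9 AM and 5 PM, and 3 weeks.

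Both POD2 resting-pain cells carry footnote b: "If patient has been discharged before this time point assessments will not be collected". The text of Section 4.6 lists scores "in the morning and afternoon on postoperative day one and two and at the post-operative clinic visit" and mentions no exception for discharge. On method it says "The patient will record their pain on a data collection form that is given to them at each time point". No section describes collecting a POD2 score from a patient who has gone home.

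On analysis, Section 4.7 says "VAS Pain scores (resting, ambulating) will be compared between groups at each time point using a Mann-Whitney Rank Sum test", with a threshold of .0083 at each time, and "Missing data will be treated as such; there will be no imputation".

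Readiness for discharge in Section 4.6 has eight criteria. One is "A pain score of <4 (numeric rating scale) without non-oral narcotics". On timing: "Readiness for discharge will be assessed in both the morning and evening of each postoperative day".

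**The concern.** Ordinary missing scores cost precision. Here the reason for a missing score may be the outcome itself: a patient with low pain is more likely to meet the readiness criteria and leave. If the block works, more block patients would leave, and those left would be selected more strongly for high pain than those left in the control arm. The POD2 comparison then conditions on something that happened after randomisation, and randomisation no longer protects it.

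Three things are at stake for one third of the primary tests:

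- Power falls because fewer patients are compared.
- A true POD2 benefit may look smaller than it is.
- A difference may appear where none exists. This can happen if discharge differs greatly between arms. It can also happen with one discharge pattern in both arms, if the block lowers POD1 pain but not POD2 pain. In that second case the error runs against the block and would look like a false late disadvantage.

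The plan does not limit the POD2 conclusions to inpatients, ask for retention by arm, or include a sensitivity analysis for discharge. The scores at 3 hours, on POD1 and at 3 weeks are not affected.

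**Working it through.** **The plan's own figure.** Table I has six postoperative resting-pain cells, two with footnote b (2/6 = 33%). The threshold .05/6 = .00833 reproduces the stated .0083. Section 4.7 states two-sidedness only for the unadjusted tests; two-sided is assumed here. Section 4.7.1 gives no effect size, SD or power, so there is no sample size to reproduce.

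**Which time is more exposed.** The Table I windows are 7–11 AM (9 AM ± 2 h) and 2–8 PM (5 PM ± 3 h). The 9 AM score is lost mainly by leaving on POD1. The 5 PM score is lost by those same patients and by anyone leaving on POD2 morning, so loss at 5 PM is at least as large.

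**Effect of smaller numbers alone.** The detectable difference at 80% power, in SD units, is (2.638 + 0.842) × √(2/n):

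| n per arm | Detectable difference (SD) | Power for 0.7 SD |
|---|---|---|
| 50 | 3.480 × 0.200 = 0.70 | 81% |
| 40 | 3.480 × 0.224 = 0.78 | 69% |
| 25 | 3.480 × 0.283 = 0.98 | 44% |
| 15 | 3.480 × 0.365 = 1.27 | 24% |

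**Effect of selection, by simulation.** Assumed, not in the documents: 50 per arm; bivariate normal POD1 and POD2 pain, rounded and clipped to 0–10; control mean 4; SD 2.2; correlation 0.6. A stated share of patients with POD1 pain below 4 leaves, chosen at random to stand in for the other seven criteria. The test is Mann-Whitney at .05/6.

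Check on the numbers left: with rounding, pain below 4 means a latent value below 3.5. In control that is Φ((3.5 − 4)/2.2) = 0.41; with a latent shift of −1.5 it is Φ((3.5 − 2.5)/2.2) = 0.675. At 50% discharge, 50 × (1 − 0.5 × 0.675) = 33 block and 50 × (1 − 0.5 × 0.41) = 40 control patients remain.

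(a) *True difference −1.39 on both days* (20,000 trials per row; full-data power 72%):

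| Low-pain patients who leave | Left, block v control | Observed difference | Power | Power if the same numbers were lost at random |
|---|---|---|---|---|
| 10% | 47 v 48 | −1.40 | 69% | 69% |
| 30% | 40 v 44 | −1.39 | 61% | 61% |
| 50% | 33 v 40 | −1.38 | 51% | 53% |
| 80% | 23 v 34 | −1.23 | 28% | 37% |
| 100% | 16 v 29 | −0.90 | 10% | 25% |

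Varying the correlation from .4 to .8 or the control mean from 3 to 5 gives power of 49–52% at 50% discharge, 24–34% at 80% and 4–20% at 100%.

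(b) *Benefit of −1.39 on POD1, none on POD2, same rule in both arms* (40,000 trials). At 30/50/80/90/100% discharge the spurious POD2 difference is 0.00, +0.04, +0.22, +0.36 and +0.59. Rejection is 0.8, 0.8, 1.2, 1.9 and 3.7% against a nominal 0.83%. From 80% upward nearly all rejections go against the block. At 100%, rejection ranges from 1.7 to 10.2% for correlations .4 to .8.

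(c) *No effect on either day, unequal discharge, control v block* (40,000 trials). Rejection is 0.9–1.1% at 30 v 10, 50 v 30, 70 v 50 and 90 v 80%. It is 2.8% at 90 v 50% (difference −0.40) and 5.1% at 90 v 30% (−0.54). Nothing in the documents supports splits that large.

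(d) *9 AM against 5 PM* (20,000 trials). Suppose 10% of low-pain patients leave on POD1 evening, then 50% (or 80%) of low-pain patients leave after the POD2 9 AM score. At 9 AM, 47 v 48 remain and power is 69%. At 5 PM, 31 v 38 (22 v 33) remain and power is 47% (26%).

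**The case against.** The case on the other side has real force.

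- *This is a declared schedule, not a contradiction.* Section 4.6 defines the primary outcome by reference to Table I, which carries the footnote. That stands: the narrative should be aligned, but it is not a second error.
- *Exposure may be small.* No discharge rate is given. The opioid outcome for 24–48 h in hospital and the exploratory exclusion of stays over 3 days both suggest that some patients stay to POD2. That stands too, and is why the point is worded as a possibility.
- *The discharge model is harsh.* In it, no patient with pain of 4 or more leaves, yet readiness is listed as an outcome and no section says actual discharge follows it. If patients with pain of 4 or more leave at half the rate, then at 80% the observed difference in (a) is −1.34 rather than −1.23, the spurious difference in (b) is about +0.11, and rejection is about 0.8%. More patients are lost, however, so power falls further.
- *The stated hypothesis is hardly touched.* With the same inputs extended to both POD1 and both POD2 scores (3 hours and 3 weeks left out; 3,000 trials), power for at least one significant time is 92% with full data and 90, 88 and 86% at 50, 80 and 100% discharge. This is useful context. It assumes a benefit that is already present on POD1; a benefit confined to POD2 would be hit harder.

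None of this removes the defect. Each POD2 test is a primary test that can support a claim by itself, and as planned the reader could not tell whom it describes.

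**Conclusion.** The concern holds; it should be fixed, with medium confidence. Two of the six primary tests, chiefly POD2 5 PM, may compare only patients still in hospital, and the plan neither says so nor examines it.

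Under the assumed inputs, the cost up to about 50% discharge of low-pain patients is almost entirely lost numbers: single-test power 51% against 72%. Dilution of the effect becomes material at 80–100%. False positives stay near the nominal 0.83% unless discharge is extensive or very unequal between arms. The actual size and direction cannot be determined, because the documents give neither discharge rates nor a rule linking readiness to discharge. This is an avoidable weakness in the POD2 results and not a demonstrated threat to the trial's overall conclusion.

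**What to change.** **Preferred.** Remove footnote b for the pain scores. At discharge, give each patient the same self-completed form for any remaining POD2 times, with date and time entered by the patient and judged against the Table I windows. If a reminder call is used, the caller should not know the allocation (under Section 4.4 the consenting personnel assign groups and keep the logs), and the patient should give the score. Align Section 4.6 with Table I, including its wording on when the form is handed over.

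**In either case.** Report by arm, at each POD2 time, the number assessed, the number already discharged and the number missing for other reasons. Length of stay, already collected, would let a reader recover only part of this. Footnote b also covers POD2 ambulating pain, the Quality of Recovery-40 and the symptom distress scale, so give the same counts for them.

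**If scores are not collected after discharge.** State in Section 4.7 and in the conclusions that the POD2 tests apply only to patients still in hospital. Add a sensitivity analysis with a repeated-measures model using all observed scores. It is valid only if discharge depends on recorded earlier pain. In the simulation, where that holds by construction (6,000 trials), a likelihood estimate gave −1.40, −1.41 and −1.43 in case (a) at 50, 80 and 100% discharge (power 60, 46 and 30%). In case (b) it gave +0.02, +0.04 and +0.06, with rejection of 0.7–0.8%.

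**Optional.** Take POD2 out of the confirmatory family and amend Section 3.0. The threshold becomes .05/4 = .0125. By normal approximation, power per remaining test rises from Φ(3.22 − 2.638) = 72% to Φ(3.22 − 2.498) = 76%, but any POD2 claim is given up even if few patients leave.

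**Cost.** At most two short forms per discharged patient (2 × 100 = 200 at the very most), edits to Table I and Sections 4.6 and 4.7, and ethics and consent updates if needed. No extra patients or procedures. Some scores will be late or missing, and home scores will be mixed with hospital scores while pain medication is recorded only in hospital. Scores not collected at the time cannot be recovered later.
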